7.3.4. Study Population

The study population will include male PwSHA without a history of (or current) inhibitors to FVIII in Germany. Participants will be identified from the DHR (see Section 7.5.1 for further description of the DHR) and are expected to provide written informed consent to be included in this study. Participants will be captured in either the Roctavian or SoC Cohorts based on the treatment they receive during the study recruitment window. The study aims to enroll at least 67 PwSHA into the Roctavian Cohort and at least 330 PwSHA into the SoC Cohort. The therapeutic treatment strategy for an individual who consents to this study is made independently of the decision to participate in the study and enrollment into this study will not inform the treatment strategy.

Participants will be selected into one of two mutually exclusive Cohorts based on the treatment they receive for HA. The Roctavian Cohort will include participants who received Roctavian during the recruitment period. The index date for these participants will be the date Roctavian is administered. The SoC Cohort will include participants who received prophylactic treatment with any of the following SoC treatments, recombinant or human plasma-derived (PD) blood coagulation FVIII or emicizumab. Participants in the SoC Cohort cannot have a history of exposure to Roctavian. Eligibility criteria will be confirmed at time of enrollment based on DHR field that the participant fulfills the AbD inclusion/exclusion criteria.

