7.6. Study Sample Size

The primary goal of HA treatment is to reduce the bleeding rate or to achieve freedom from bleeding. As an approximation of the appropriate number of cases for the data collection accompanying the application, the Institute for Quality and Efficiency in Health Care (IQWiG) conducted the sample size calculation based on ABR for treated bleeds. Evaluation of the ABR is performed using a negative binomial model.

The formula for The sample size calculation is as follows:

$$N_1 \geq \frac{(z_\alpha \sqrt{V_0} + z_\beta \sqrt{V_1})^2}{(\log(R_0) - \log(\lambda_2/\lambda_1))^2}$$

$$N_2 = \theta N_1$$

Where:

$$V_1 = \frac{1}{\mu_t} \left(\frac{1}{\lambda_1} + \frac{1}{\theta \lambda_2} \right) + \frac{(1 + \theta)\varphi}{\theta}$$

V_0 is computed using the fixed marginal total method, the 2nd method recommended by Zhu et al.:²⁷

$$V_{02} = \frac{(1 + R_0\theta)^2}{\mu_t R_0 \theta (\lambda_1 + \theta \lambda_2)} + \frac{(1 + \theta)\varphi}{\theta}$$

N_1 is the sample size for control, N_2 is the sample size for intervention. $\theta = \frac{N_2}{N_1}$, which is the sample size ratio; R_0 is the superiority margin ratio at the null hypothesis. In this case, R_0 is <1 since higher rates are worse. λ_1 is the event rate in the control group, and λ_2 is the event rate in the intervention group. φ is the dispersion parameter, and μ_t is the average exposure time. z_α is the z-score at the significance level, z_β is the z-score at the power value.

When higher rates are worse, the superiority by a margin test hypotheses are

$$H_0: \frac{\lambda_2}{\lambda_1} \geq R_0 \quad \text{vs.} \quad H_1: \frac{\lambda_2}{\lambda_1} < R_0$$

Where $R_0 < 1$.

The relative effect measure is the incidence rate ratio of Roctavian over SoC, which can be tested against the shifted null hypothesis of 0.5, assuming a significance level $\alpha = 2.5\%$ with a one-sided test, and power of at least 80%. Higher values for the ABR (parameter λ) stand for a worse outcome. Furthermore, a distribution of the Sample Roctavian vs. SoC of 1:5 is assumed (sample size ratio $\theta = 0.2$). Other required parameters are the Average Exposure Time ($u_t = 1$ year), the ABR for the SoC and Roctavian groups ($\lambda_{SoC} = 3$, $\lambda_{Roctavian} = 0.85$) and a value for the overdispersion ($\phi = 1.5$). This results in a total sample size of at least 397 participants (Roctavian Cohort $n = 67$, control Cohort $n = 330$).

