7.9. Statistical Analysis Approaches

Descriptive statistics will be generated for all study measures. Descriptive statistics will include means, 95% CIs, SDs, medians, interquartile range (IQR), and minimum and maximum values for continuous variables and frequencies and percentages for the categorical variables. Univariate statistics will be calculated for each measure of interest. Baseline and outcome variables will be compared between the Roctavian and SoC Cohorts using chi-square tests for categorical variables, two-sided t-tests for continuous variables, and Wilcoxon rank-sum tests for medians of continuous variables if the continuous variables are not normally distributed.

For event-based outcomes including the bleeding outcomes, negative binomial models will be fit. Zero-inflated negative binomial models will also be considered if the outcomes show excess zeros (see Section 7.9.3 for details). For binary outcomes, logistic regressions will be fit. For continuous outcomes, general linear regression will be used, with appropriate transformation if needed to ensure model assumptions are met. For COAs, general linear mixed models to account for repeated measures are planned. All the models will be adjusted with propensity score weights and results will be reported based on observed values (before IPTW is applied) and the weighted values (after IPTW is applied).

To adjust for confounding, propensity scores will be calculated and applied using appropriate propensity score IPTW to ensure balance of covariates between the Roctavian and SoC Cohorts. Both unadjusted and propensity score adjusted results will be reported. IPTW is the primary propensity score method for adjustment of confounding. PSM will be performed as an *a priori* sensitivity analysis. Additional details on propensity score methodology is presented in Section 7.8. If additional covariate adjustment is required to balance the Cohorts, multivariable models will be reported.

P-values and SMDs will be reported for comparisons between Roctavian and SoC Cohorts. A p-value <0.05 will be considered statistically significant. All analyses will be based on observed, not projected, data. The sample size calculations are powered for the primary outcome (i.e., ABR), therefore, all p-values associated with secondary outcomes are nominal.

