7.9.2. Analysis of Baseline Characteristics

Descriptive analysis will be conducted to describe baseline demographic and clinical characteristics of the Roctavian and SoC Cohorts. See Table 3 for a list of all variables that will be described for the two Cohorts. The baseline characteristics will capture data before the index date.

Measures of central tendency and dispersion (mean, SD, median) will be calculated and reported for continuous variables for each Cohort. Continuous variables may be categorized into intervals, with the distribution of participants (n, %) provided. Independent sample t-tests for mean values and Wilcoxon rank-sum tests for median values will be performed as a comparison between the Roctavian and SoC Cohorts.

For categorical variables, distributions and frequencies will be compiled and reported. Data will include the frequency (n, %) of total participants observed in each category. Chi-square tests will be performed as a comparison between the Roctavian and SoC Cohorts.

SMD will be calculated for both continuous and categorical variables. SMD represents a commonly used statistic to examine the balance of covariate distribution between groups, with a value greater than 0.1 indicating some imbalance between groups, and SMDs >0.25 indicating poor balance.⁴⁵

Participant characteristics will be presented for all participants prior to weighting and after weighting (for Roctavian and SoC Cohorts separately), overall, and for subgroups and sensitivity analyses where appropriate. Participant characteristics prior to and after weighting will be compared using the statistical tests noted above to capture differences between the observed population and the weighted target population.

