7.9.4.4. Clinical Outcome Assessments

Population	Measurement Period	Analysis Notes
All participants with sufficient follow-up, comparing Roctavian Cohort to SoC Cohort; Participants without any COA scores will not be included	Assessments are expected to be conducted at baseline and every 6 months for quality of life and pain, and for joint health at least annually	For analyses of change from baseline, participants are expected to have baseline and at least one follow-up measure

The Hemophilia Joint Health Score (HJHS), Haemo-QoL-A, and Brief Pain Inventory – short form (BPI-sf) will be used as COAs. As these instruments standardize collection of data for areas that are monitored in routine clinical practice, the assessments are expected to follow routine clinical follow-up. Physicians participating in the AbD are expected to enter data for these instruments collected relative to the study index date per the operational definitions outlined in Table 5. The following Table 8 includes the assessment timepoints of interest throughout the follow-up and tolerance windows. If a participant has multiple measurements reported in the same window, the measurement closest to the time point of interest will be selected. An individual data point will only be utilized once in the analysis (e.g., if there is a measure at 1.2 years, this data point would only be used for 1 year and not the 2 year analysis).

Table 8. COA Timepoints of Interest and Tolerance Windows

Timepoints of Interest	Day of Assessment	Tolerance Window ¹
Baseline	Index date, day 0	0-91 days
6-months	Day 182	92-273 days
12-months (1 year)	Day 365	274-456 days
18-months	Day 547	457-638 days
24-months (2 years)	Day 730	639-821 days
30-months	Day 912	822-1,003 days
36-months (3 years)	Day 1,095	1,004-1,185 days

1. Tolerance windows are +/- 3 months before and after the expected assessment day.

Note: HJHS assessments will be completely annually, while Haemo-QoL-A and BPI-sf assessments will be completed every 6 months.

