Descriptive statistics (mean, SD, median, IQR, minimum, maximum) will be used to summarize the COA scores at baseline, follow-up, and change from baseline. Two-sided t-tests will be used to compare the absolute change in scores from baseline between Roctavian and SoC Cohorts. Distribution of the outcome variables will be checked to make sure the assumptions of the two-sided t-test are met. If a skewed distribution is observed, a non-parametric Wilcoxon signed-rank test will be performed instead. SMD of the scores at baseline, follow-up, and change from baseline between the Roctavian and SoC Cohorts will also be estimated as the effect size measure.⁴⁸ SMD values will be classified into small, medium, large or very large based on the following ranges, 0.2-0.5, 0.5-0.8, 0.8, and ≥1.3.

Participants with an evaluable baseline score and at least one evaluable post-baseline score will be included in the change from baseline analyses. Since participants are expected to have follow-up visits every 6-months for Haemo-QoL-A and BPI-sf and annual follow-up visits for HJHS, it is expected that COAs will be measured with a maximum of seven time points for Haemo-QoL-A and BPI-sf (baseline, 6±3, 12±3, 18±3, 24±3, 30±3, and 36±3 months) and four time points (baseline, 12±3, 24±3, and 36±3 months) for HJHS. The last follow-up measure will be used in the change from baseline analysis. The last follow-up measure may be required to have occurred at least a certain

number of years after baseline to increase interpretability of results. A general linear mixed model with unstructured covariances will be fit to conduct a longitudinal analysis for each COA outcome. The mixed model is chosen to account for the repeated measures, while allowing flexibility for any potential missing values. No missing data will be imputed. The explanatory variables that will be included in the model are treatment (Roctavian vs. SoC) and time. Treatment by time interaction will also be included in the model to assess whether the treatment effect changes across time. Residual analysis will be conducted to ensure the independent and identically distributed random variables assumptions of the model residuals are met. Regression coefficients, 95% CIs and P-values for each of the fixed-effects parameters will be reported. Estimated correlation matrix will also be reported to assess the correlation of the outcome between each time point.

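### The skewed-data fallback for change in HJHS, Haemo-QoL-A and BPI-sf is a signed-rank test, which does not compare Roctavian with SoC and conflicts with the rank-sum test named elsewhere in the SAP

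*Protocol*

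**What the plan says.** SAP 7.9.4.4 first states the comparison: "Two-sided t-tests will be used to compare the absolute change in scores from baseline between Roctavian and SoC Cohorts". It then asks for the distributional assumptions of that test to be checked and gives the fallback: "If a skewed distribution is observed, a non-parametric Wilcoxon signed-rank test will be performed instead". The rule covers three instruments: "The Hemophilia Joint Health Score (HJHS), Haemo-QoL-A, and Brief Pain Inventory – short form (BPI-sf) will be used as COAs". SAP 7.9.4.4.1 to 7.9.4.4.3 each refer back to 7.9.4.4 for methods, so all three inherit it.

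Two other places give a different non-parametric test. For baseline and outcome variables in general, SAP 7.9 specifies "Wilcoxon rank-sum tests for medians of continuous variables if the continuous variables are not normally distributed". For baseline characteristics, SAP 7.9.2 says "Independent sample t-tests for mean values and Wilcoxon rank-sum tests for median values will be performed as a comparison between the Roctavian and SoC Cohorts".

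The cohorts are independent groups. SAP 7.3.4 says "Participants will be selected into one of two mutually exclusive Cohorts based on the treatment they receive for HA", and SAP 7.6 plans for 67 Roctavian and 330 SoC participants.

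**The concern.** The baseline-to-follow-up pairing within a person is used up once the change score has been formed. A signed-rank test on change scores then has only one question left: are the changes symmetric about zero? It takes no cohort label. It cannot be run as a paired test across cohorts either, because nothing links a Roctavian participant to an SoC participant and the group sizes differ. The text says the test is done in place of the t-test, so under the fallback no between-cohort test of change scores would remain.

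This matters most for HJHS. Protocol 10.3.7.4 uses the repeated-measures model there to describe the trend, and makes mean change from baseline to the final assessment the comparison between cohorts. For Haemo-QoL-A and BPI-SF the same section gives the comparison to the repeated-measures model, so less depends on the change-score test.

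If the fallback were programmed as written, a change common to both cohorts could be read as a treatment difference, and a real difference could be missed.

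**Working it through.** **1. The texts side by side.**

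| Place | Comparison | Non-parametric test named |
|---|---|---|
| SAP 7.9 | Baseline and outcome variables, Roctavian vs SoC | Rank-sum |
| SAP 7.9.2 | Baseline medians, Roctavian vs SoC | Rank-sum |
| SAP 7.9.4.4 | Change in COA scores, Roctavian vs SoC | Signed-rank |

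The shells in SAP Annex 12.1 (Tables 10 to 12) head the p-value column as Roctavian versus SoC. A signed-rank p-value cannot fill that column. The contradiction is complete at this point; the remaining steps only illustrate its size.

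**2. Cohort sizes.** The plan gives no figure for the COA test, so the planned cohort sizes are used. They can be checked with the formula in SAP 7.6, using R0 = 0.5, rates 3 and 0.85, dispersion 1.5, exposure 1 year, ratio 0.2, one-sided alpha 2.5% and power 80%:

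- V1 = 1/3 + 1/(0.2 × 0.85) + (1.2 × 1.5)/0.2 = 15.216
- V0 = (1 + 0.5 × 0.2)² / [0.5 × 0.2 × (3 + 0.2 × 0.85)] + (1.2 × 1.5)/0.2 = 12.817
- N1 = (1.960 × √12.817 + 0.842 × √15.216)² / (ln 0.5 − ln(0.85/3))² = 328.8, so 329
- N2 = 0.2 × 328.8 = 65.8, so 66

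The total is 395, within 2 of the stated 397 (67 + 330). The stated sizes are used below.

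**3. Illustrative simulation.** Assumptions, none of them from the documents: right-skewed lognormal change scores with SD 1, centred so that the signed-rank null holds when the shift is zero; two-sided 5%; 2,000 replicates. SAP 7.9.4.4 does not say how a signed-rank test would be applied to two cohorts, so three versions are shown. Entries are rejection rates.

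| Shift in SD (Roctavian, SoC) | Signed-rank, pooled | Signed-rank, Roctavian only | Signed-rank, SoC only | Rank-sum |
|---|---|---|---|---|
| 0, 0 | 6.4% | 6.0% | 6.2% | 5.4% |
| 0.3, 0.3 | 100% | 98.2% | 100% | 5.2% |
| 0.5, 0.5 | 100% | 100% | 100% | 4.0% |
| 0.5, 0 | 78.8% | 100% | 6.5% | 100% |
| 0.4, −0.0812 | 7.7% | 100% | 38.8% | 100% |

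In rows 2 and 3 the cohorts do not differ, yet every signed-rank version rejects almost always. In the last row they differ by 0.4 + 0.0812 = 0.48 SD while the pooled mean shift is zero (67 × 0.4 = 26.8 and 330 × 0.0812 = 26.8), and the pooled version rejects in 7.7%.

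**4. How far the rates depend on the assumptions.** The 0.5, 0 row was repeated with gamma (shape 2) scores, SD 1, 1,000 replicates. The pooled signed-rank test rejected in about 9% when scores were centred on the mean, about 97% with the skew reversed, and about 98% when centred on the median. With mean-centred gamma scores and no shift in either cohort it already rejected in 63%. No single rate is therefore a property of the plan.

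**The case against.** The strongest reply is that this is a slip of one word. The preceding sentence fixes the comparison as between cohorts, two other sections name the rank-sum test, and the shells expect a between-cohort p-value. A paired call on 67 and 330 values will not run, so independent double-programming might expose it. All of this is fair, and a slip is the likeliest explanation. It does not make the text right: an outcome-specific rule would ordinarily take precedence over a general one, and two programmers could both code a one-sample test to specification.

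Propensity score matching might also be offered as a source of pairs. A 1:1 match could support a signed-rank test of within-pair differences. But SAP 7.9.4.4 asks for unweighted and IPTW-weighted COA analyses and describes no pairing.

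Three stronger readings are tempting and are not supported.

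- A reader might infer that the whole objective on joint health, quality of life and pain would rest on the wrong p-value. It would not. SAP 7.9.4.4 also fits a mixed model with treatment and treatment-by-time terms, reports standardized mean differences and gives responder risk ratios. All are between-cohort contrasts, and SAP 7.9 makes secondary p-values nominal.
- A reader might infer that the fallback will probably be used. The documents give no COA score distribution and no threshold for skewness, so this is unknown.
- A reader might infer that the test would generally miss an effect confined to Roctavian. Step 4 shows that this depends on the skew and centring assumed, and the plan never says that the cohorts would be pooled.

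**Conclusion.** The fallback is wrong as written. The signed-rank test does not address the comparison that SAP 7.9.4.4 sets, and it conflicts with SAP 7.9 and 7.9.2. This conclusion rests on the text and on what the test does, not on the simulation. The simulated rates show only that errors can occur in both directions; they depend on the assumed distribution and implementation.

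The reach is narrow: the fallback test of change scores for three instruments, only if skewness is observed. HJHS is the most exposed because protocol 10.3.7.4 makes mean change its between-cohort comparison. The mixed model, standardized mean differences, responder analyses, primary endpoint and sample size are untouched. This should be fixed, but it does not threaten the study's main conclusion.

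**What to change.** In SAP 7.9.4.4, replace the signed-rank test with a Wilcoxon rank-sum test comparing change from baseline between the cohorts, in line with SAP 7.9 and 7.9.2.

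The same section requires IPTW-weighted COA results, and the ordinary rank-sum test takes no weights. Either name a weighted rank test or state that the treatment contrast from the weighted mixed model serves as the weighted result.

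The cost is a short text edit, with no new data and no change to sample size. Protocol 10.3 has the SAP finalized before the data cut for the 18-month interim analysis. Making the edit before then avoids choosing between conflicting rules after the data have been seen.

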Descriptive statistics will be used to summarize the absolute and change from baseline at the time of an assessment for the total and domain scores for the Haemo-QoL-A and the BPI-SF. For the BPI-SF the pain interference and pain intensity scores will be taken as the domains. A repeated measurement analysis model will be used to compare the changes in scores between the treatment groups. Participants with an evaluable baseline score and at least one evaluable post-baseline score will be required for the specific analysis be included in the change from baseline analyses.

In addition, responder analyses will be considered for improvement and deterioration for the BPI-SF pain interference and pain intensity scales. The BPI-SF pain intensity score will be defined as the Question 5 “average pain”. The BPI-SF pain interference score will be defined as the average to all 7 subitems of Question 9 (9A to 9G).

All analysis details and scoring methods will be described in the SAP. It is expected that no missing data will be imputed.

All PROs comparisons will be interpreted after 3 years of follow-up, or latest available follow-up score if a full 3 years of follow-up is not available.

10.3.7.5. Objective: To compare safety events of interest.

Safety events outlined in [Table 8](#) will be described in each cohort. Summaries of the proportion, event rate, and incidence rate of each of the safety events among all participants by cohort will be provided. Safety events will be described from index through follow-up. All participants will be included in analyses of event and incidence rates, while analyses of the proportion of participants will only include those participants with follow-up for the full time over which the proportion is calculated. Safety outcomes will be compared as relative risks based on the incidence of an event for analyses of the treatment policy estimand and as incidence rate ratios censoring a participants person time at the time of the event for analyses of the hypothetical estimand.

10.3.7.6. Objective: To describe time to resumption of prophylactic treatment among participants administered Roctavian

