Variable	Found by literature review	From previous PS work	Clinical expert opinion	Considerations
Baseline/prior bleeding history (e.g., ABR)	✓	✓	✓	Include regardless of statistical association, based on clinical relevance
Baseline FVIII utilization	✓	✓	✓	Include based on statistical association and correlation with other variables (e.g., baseline/prior bleeding history and baseline prophylaxis class)
Baseline prophylaxis class (FVIII vs. emicizumab)	✓	✓	✓	Include based on statistical association and correlation with other variables (e.g., baseline/prior bleeding history and FVIII utilization)
Age	✓	✓	✓	Include based on statistical association
Height, Weight and/or BMI	✓	✓	✓	Include based on statistical association
Baseline von Willebrand factor (IU/mL)	✓	X	✓	Include based on statistical association
Number of target joints	✓	✓	X	To be considered depending on statistical association and correlation with other variables (e.g., baseline/prior bleeding history and joint health score)
Joint health (e.g., baseline/prior HJHS)	X	X	✓	To be considered depending on statistical association and correlation with other variables (e.g., baseline/prior bleeding history and number of target joints)
Baseline/prior type of bleeds	X	X	✓	To be considered depending on statistical association and correlation with other variables (e.g., baseline/prior bleeding history and target joints)
Geography (HTC/site/region/country)	✓	✓	X	Site to be considered depending on statistical association and correlation with other variables
Prophylaxis class switching (e.g., SHL/PD to EHL/emicizumab)	✓	✓	X	To be considered depending on statistical association and correlation with other variables
Baseline/prior pain (e.g., BPI-sf)	X	X	✓	To be considered depending on statistical association and correlation with other variables (e.g., target joints and HJHS)

Variable	Found by literature review	From previous PS work	Clinical expert opinion	Considerations
Baseline/prior QoL (e.g., haemo-QoL-A)	X	X	✓	To be considered depending on statistical association and correlation with other variables
Activity status	X	X	✓	Not considered as this there is no validated questionnaire for lifestyle factors in PwSHA
Baseline/prior history of liver fibrosis/cirrhosis	✓	X	X	Significant liver fibrosis/cirrhosis is accounted for by the exclusion criteria, but less severe liver fibrosis to be considered based on statistical association

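### The mixed model for joint health, quality of life and pain does not use the baseline score as a covariate, which costs precision and leaves the change contrast open to residual baseline imbalance

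*Protocol*

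**What the plan says.** SAP 7.9.4.4 specifies the longitudinal analysis: "A general linear mixed model with unstructured covariances will be fit to conduct a longitudinal analysis for each COA outcome". On its terms it says "The explanatory variables that will be included in the model are treatment (Roctavian vs. SoC) and time", and then "Treatment by time interaction will also be included in the model to assess whether the treatment effect changes across time". The shells in SAP Annex 12.1, Table 13, carry these same terms in both the unadjusted and the adjusted versions, with no row for baseline. Beside the model stands a simple test: "Two-sided t-tests will be used to compare the absolute change in scores from baseline between Roctavian and SoC Cohorts".

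A baseline score is a condition of entry: "Participants with an evaluable baseline score and at least one evaluable post-baseline score will be included in the change from baseline analyses". Baseline also appears in the list of assessment times, a "maximum of seven time points for Haemo-QoL-A and BPI-sf (baseline, 6±3, 12±3, 18±3, 24±3, 30±3, and 36±3 months"), with four for HJHS. Protocol 10.3.7.4 describes the aim for Haemo-QoL-A and BPI-SF as a comparison of change: "A repeated measurement analysis model will be used to compare the changes in scores between the treatment groups".

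SAP 7.9.4.4 runs these analyses both unweighted and with inverse probability of treatment weights (IPTW). In SAP Table 6 the baseline HJHS, BPI-SF and Haemo-QoL-A scores are candidates for the propensity score with the remark "To be considered depending on statistical association and correlation with other variables". Only prior bleeding history is included whatever its statistical association.

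**The concern.** A participant's own baseline score is usually the strongest measured predictor of the later score on the same instrument. The plan requires it for the change analyses, yet uses it neither as a covariate in the mixed model nor in the t-test. Two things are at stake.

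- **Precision.** With about 67 to 70 treated participants, intervals for the cohort contrast may be wider than the data require.
- **Imperfect weights.** If a baseline score is not selected into the propensity score, or is selected and still poorly balanced, nothing in the COA model picks up the remainder.

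The plan's other safeguards reach this model only loosely. SAP 7.8.1 selects the propensity model by backward stepwise regression, and SAP 7.9.5.1 drops a covariate with more than 40% missing. SAP 7.8.2.3 calls a standardized mean difference (SMD) above 0.1 some imbalance but refines the propensity model only above 0.25. It then moves still-imbalanced covariates into the outcome regression with bleeding events as the named case. Clauses that add imbalanced covariates are written for the bleeding rates, zero bleeds, responders and safety, but not for the COA mixed model.

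**Working it through.** **The plan's own figure.** No sample size or power is stated for the COA model. The only powered figure is the total of 397 for the bleeding rate (SAP 7.6). With that section's formula and inputs (rates 3 and 0.85, θ = 0.2, φ = 1.5, exposure 1 year, R0 = 0.5, one-sided 2.5%, power 80%):

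- V1 = 1/3 + 1/(0.2 × 0.85) + 1.2 × 1.5/0.2 = 15.22
- V0 = 1.1²/(0.5 × 0.2 × 3.17) + 9 = 12.82
- N1 = 328.8 and N2 = 65.8, so 329 + 66 = 395, close to the stated 330 + 67 = 397.

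Those group sizes are used below.

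**Inputs not in the documents.** The correlation r between baseline and follow-up is assumed, over 0.5 to 0.9. The residual baseline difference d is taken at the SAP's two thresholds, 0.10 and 0.25 SD. Scores are scaled to SD 1 at both times.

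**Step 1: precision.** Per-participant variance is 2(1 − r) for change and 1 − r² after baseline adjustment. The ratio is (1 + r)/2, a reduction of (1 − r)/2. Power is for an illustrative difference of 0.3 SD, two-sided 5%, 330 against 67, ignoring the information lost through weighting.

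| r | Change | Adjusted | Reduction | Power, change | Power, adjusted |
|---|---|---|---|---|---|
| 0.5 | 1.00 | 0.75 | 25% | 61% | 73% |
| 0.7 | 0.60 | 0.51 | 15% | 82% | 88% |
| 0.8 | 0.40 | 0.36 | 10% | 94% | 96% |
| 0.9 | 0.20 | 0.19 | 5% | 99.9% | 99.9% |

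The gain is smaller if the score is already in the propensity score.

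**Step 2: leak of a residual difference, under exchangeability.** Suppose there is no treatment effect and follow-up is independent of cohort given the baseline score. A baseline difference d then becomes r·d at follow-up, so the change contrast is r·d − d = −d(1 − r).

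| r | d = 0.25 | d = 0.10 |
|---|---|---|
| 0.5 | 0.125 | 0.05 |
| 0.7 | 0.075 | 0.03 |
| 0.8 | 0.05 | 0.02 |
| 0.9 | 0.025 | 0.01 |

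(Absolute size in SD.) A simulation of 20,000 data sets per value of r at d = 0.25 gave mean change contrasts of −0.124, −0.074 and −0.049 at r = 0.5, 0.7 and 0.8, and 0.000, 0.001 and 0.001 after adjustment. It builds in the same assumption, so it confirms the algebra and not the assumption.

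**Step 3: the opposite assumption.** Suppose the cohorts differ by a stable d at both times, with no effect. The change contrast is d − d = 0. The adjusted contrast is d − r·d = d(1 − r), the same amount now produced by adjustment.

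**Step 4: baseline as a response time point.** The list of time points allows this reading. With treatment, time and an unconstrained interaction, every cohort-by-time mean is free. In complete data the contrast in change from baseline is then the plain difference in mean change, so Steps 1 and 2 still apply. Nothing in the text constrains the cohorts to a common baseline mean.

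**The case against.** The strongest case concerns bias. These cohorts are self-selected, and Step 3 shows that adjustment can create the same spurious contrast that it removes in Step 2. Protocol 10.5 itself says that these measures are best described by comparison within the participant, which gives change scores a stated rationale. Evaluating the leak at d = 0.25 also supposes that weighting has worked poorly. This stands in part: neither analysis dominates without an assumption. The plan's assumption is nevertheless that the cohorts are comparable given measured covariates (SAP 7.8.1 and 7.8.3; Protocol 10.5), and under it conditioning on the baseline score is the coherent choice.

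A reader might infer more than the documents support:

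- **That the omission biases the COA results outright.** It does so only under the Step 2 assumption and with a residual imbalance.
- **That baseline is absent from the analysis.** It is required, it is listed as a time point and may be part of the response, and its SMD is tabulated before and after weighting, so an imbalance would be visible.
- **That nothing can be done below an SMD of 0.25.** SAP 7.9 has a general fallback of multivariable models if balance requires it, although it gives no trigger and the COA model text does not take it up. The responder models may already add imbalanced covariates.
- **That the loss is large.** At r of 0.8 to 0.9 it is 10% to 5% of variance.

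**Conclusion.** The point holds as a matter of precision, with a conditional point on bias. The specified model and t-test do not use the baseline score as a covariate, the response variable is left unstated, and the baseline scores are not assured of a place in the propensity score.

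The avoidable variance is 25% to 5% for r from 0.5 to 0.9, less if the score is already in the propensity score. The possible leak is 0.03 to 0.13 SD at a residual SMD of 0.25 and 0.01 to 0.05 SD at 0.10. It rests on exchangeability given measured covariates; with stable cohort differences the change score would be unbiased and the adjusted contrast would not. The correlation is assumed throughout.

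The outcomes are secondary and SAP 7.9 treats their p-values as nominal. The primary bleeding-rate result is not touched.

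**What to change.** In SAP 7.9.4.4, name the response and make the IPTW-weighted COA model one of post-baseline scores with treatment, visit, treatment-by-visit, baseline score and baseline-by-visit, using robust standard errors. Update the Table 13 shells to match. Keep the planned change-from-baseline analysis as a sensitivity analysis, and say that the two rest on different assumptions, so that a disagreement between them is informative.

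No new data are needed, and the population is the one already required: a baseline and at least one follow-up score. The cost is a modest amount of extra analysis, revised shells and open reliance on exchangeability given measured covariates. Protocol 10.3 has the SAP finalised before the first data cut for the 18-month interim analysis, so the change belongs before then.
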